Inhaled Mometasone to Promote Reduction Of Vaso-occlusive Events Trial
(IMPROVE Trial)
A feasibility study

NCT02061202
Version Date: 11-18-2015

Supplement 1: Study protocol and schedule of protocol changes

- 12/24/2013: Protocol modified to add and remove study personnel
- February, 2014: First participant enrolled
- 3/11/2014: Minor changes to case report forms
- 6/30/2014: Add investigator signatures to case report forms
- 9/16/2014: Draw an additional 5-10 cc of blood at study entry and 8-weeks to performed cell-based assays of immune activation
- 5/11/2015: Clarify color of tubes for blood collection
- 9/18/2015: Change metrocard incentive to \$11 from \$10
- 11/18/2015:
 1. The medication adherence cutoff for inclusion in per-protocol analyses was changed from 80% to 70%
 2. The original protocol included non-adherent individuals in the intent to treat analyses but did not follow them after 8-weeks (i.e. after follow up questionnaires, clinical data, spirometry, eNO and blood were collected). The protocol was modified to continue following non-adherent individuals up to 16 weeks to evaluate strategies to improve medication adherence.
- October, 2016: Data collection completed

Inhaled Mometasone to Promote Reduction Of Vaso-occlusive Events Trial
(IMPROVE Trial)
A feasibility study

Manual of Operating Procedures

**Inhaled Mometasone to Promote Reduction Of Vaso-occlusive Events Trial
(IMPROVE Trial)**

[name] MD, MA FACEP Principal Investigator Icahn School of Medicine at Mount Sinai [name] [contact] [contact] Email: [contact]
	
[name] Senior Research Coordinator Icahn School of Medicine at Mount Sinai [name] [REDACTED] [REDACTED]

[name] Research Coordinator Icahn School of Medicine at Mount Sinai [name] [REDACTED] [REDACTED]
	
[name] Senior Statistician Icahn School of Medicine at Mount Sinai [name] [REDACTED]

[name] Research Coordinator Icahn School of Medicine at Mount Sinai [name] [REDACTED] [REDACTED]
	
[name] Research Coordinator Icahn School of Medicine at Mount Sinai [name] [REDACTED] [REDACTED]

1.3.2 Meeting Schedule

Advisory board meetings will occur quarterly

1.4.2 Meeting Schedule

The DSMB will meet prior to subject enrollment and data collection and will meet at 6 month intervals thereafter

1.4.3 DSMB responsibilities

The DSMB will report Adverse Events (AEs) to the Mount Sinai Institutional Review Board, the funding I/C, the NIH Office of Biotechnology Activities (OBA), and the Food and Drug Administration (FDA) in accordance with Investigational New Drug (IND) regulations. The responsibilities of the DSMB will include: 1) overseeing the study's progress, 2) approving alterations or amendments to the study protocol, 3) monitoring safety and reviewing serious adverse events (SAE) which includes: death, intubation for acute chest syndrome, intensive care unit admission, or pulmonary infection, 4) overseeing data quality, 5) reviewing the interim analyses and recommending early trial cessation if indicated. The PI will be responsible for providing the DSMB with all necessary information.

2.1 Study organization and Responsibilities

2.2 Clinical coordinating center

The IMPROVE trial Clinical Coordinating Center (CCC) is directly responsible for the monitoring and oversight of all fiscal, regulatory, clinical and other general administration needed to centralize and coordinate the research endeavors of the IMPROVE trial. The CCC is located at the Icahn School of Medicine at Mount Sinai (ISMMS) and is led by the Study PI, [name] MD, MA. Under the PI supervision the senior research coordinator (SRC) will assist with the responsibilities of the CCC.

The responsibilities of the CCC will include:

- protocol and manual of operations development and amendments
- facilitating and monitoring protocol conduct
- overseeing regulatory compliance
- monitoring of adverse effects and events
- assuring quality control via site audits
- providing annual and quarterly reports on the progress of the IMPROVE Trial
- electing topics for investigation
- participating in the analysis and interpretation of data
- manuscript preparation and prioritization via the IMPROVE Trial Publication Policy
- plan and organize investigator and oversight meetings
- coordinate all NIH requirements related to the grant

2.3 Statistical coordinating center (SCC)

Collection and analysis of data generated for the IMPROVE trial will be coordinated by the PI and research coordinators (RCs) and will leverage the resources of the biostatistics,

epidemiology, and research design (BERD) program at ISMMS to monitor data collection. Responsibilities of the SCC will include:

- **Preparation of study documents**

SCC staff will develop: Protocol, Manual of Operating Procedures (MOP), case report forms (CRFs), and QxQs (question by question), which give the details on answering the questions on every CRF). Materials given to participants (brochure/copy of consent form) will not mention the study acronym “IMPROVE” to avoid suggestive influence of the title.

- **Statistical design and sample size**

SCC statisticians developed the statistical design for the study, including the primary outcome, sample size, randomization strategy, primary analysis strategy, and the complete analysis plan.

- **Training site personnel**

SCC staff has have trained site personnel in all aspects of the study related to: details of the study protocol, data collection procedures, screening and randomization procedures, submitting forms to the SCC, laboratory preparation procedures, and responding to queries from the SCC. SCC staff will also monitor each site to assure that the site coordinators have completed the required training.

- **Receipt and processing of study forms at the SCC**

SCC staff have designed and implemented the data management system for the study, including: electronic data entry, comprehensive editing of the data and preparation of protocol adherence aids, and data extraction for analyses related to research objectives. Data are submitted to the SCC through REDCap, a web-based data entry system. All hardcopy CRF's are maintained in a locked cabinet in a locked room. Once hardcopy enters this **storage facility**, it does not leave. Data are comprehensively edited once received at the SCC, prior to insertion into the main study database. Edit queries are resolved within a few days with the PI. The PI electronically signs off on all case report forms in REDCap before they are finalized. SCC staff also enforces patient confidentiality and privacy rules so that PHI data are not shared inappropriately and so that data are protected by multiple layers of security.

- **Monitoring study progress and data quality**

SCC staff ensures that clinic site staff are properly trained, that performance of the required procedures are monitored, and that deviations from the protocol or from study norms are investigated. Routine site monitoring reports, including patient recruitment, performance of follow-up visits, and protocol compliance, will be produced at regular intervals. For spirometry, the SRC's past 10 PFT results will be reviewed to ensure reproducibility of results.

- **Quality assurance procedures**

SCC staff will conduct quality assurance audits for every 5 participants enrolled in the study. In addition, quality assurance procedures and programs will be developed and implemented for laboratory determinations, for data collection, and for data entry.

- **Randomization**

SCC staff have developed and implemented an adaptive, biased coin, covariate balanced randomization algorithm. The algorithm is implemented using a windows laptop running the program 'R' which will be carried on the IMPROVE research cart.

After screening for eligibility is complete, participants will be randomized. The Randomization algorithm will balance participants based on whether or not they take hydroxyurea and by the number of ED visits for pain during the preceding year (this variable will be trichotomized: 0-5, 6-10, 11-15).

- **Data and Safety Monitoring Board (DSMB) functions and reports**

SCC staff will prepare reports for the DSMB and will respond to ad hoc queries from the DSMB. SCC staff developed the study monitoring plan, which indicates when interim monitoring of the efficacy outcomes will be performed, how adverse events will be reported, as well as the content of the DSMB reports. The DSMB reports will include tabulations and graphical presentation of administrative data (e.g., recruitment, compliance with therapy schedule, completion of follow-up procedures, and submission of data to the SCC), efficacy data (e.g., primary and secondary outcomes of the study, as required by the monitoring plan), and safety data (e.g., the occurrence of adverse events and serious adverse events).

- **Statistical analysis plan**

[figure not shown]
SCC staff developed the statistical analysis plan, which indicates, in detail, the main analysis for the primary outcome (including intention-to-treat analyses), secondary analyses, and analyses of the secondary and safety outcomes. In addition, the plan includes the frequency of DSMB reports, and how missing data will be handled.

- **Collaboration in study publications**

SCC staff will collaborate in all study publications, providing statistical analysis, preparing the statistical methods and results sections of manuscripts, and preparing camera-ready tables and graphs. SCC staff will also participate in the development and review of abstracts for presentations and in the review of the statistical analysis for ancillary publications.

Manual of Operating Procedures

2.2.1 IMPROVE trial organizational chart

3.0 Study overview

We will conduct a randomized, double blind, placebo-controlled, feasibility study of mometasone furoate, an inhaled cortico-steroid (ICS), for 16 weeks in individuals with SCD and recurrent cough or wheezing who do not meet clinical criteria (derived specifically for individuals with SCD) for a diagnosis of asthma. Participants will be enrolled when they are pain free and have no acute respiratory symptoms. The sample size will be 45 participants, aged ≥ 15 , with 2:1 allocation of drug to placebo. Feasibility will be determined by the proportion of individuals successfully randomized who maintain good adherence and complete at least 30 pain diaries vs. the total number enrolled.

4.1 Storage of study materials

4.2 The IMPROVE research cart

A mobile research cart will be maintained by the SRC. The research cart is equipped with a laptop, FVL machine (spirometry machine) with 3L syringe, disposable mouth pieces and nose plugs; mini centrifuge with micro tubes and pipettes. The research cart will also be stocked with study medication packets (closed envelopes which contain training materials and study medication or placebo), study binders (study logs, enrollment paperwork), and the NIOX MINO exhaled nitric oxide measuring device.

4.3 Study medication

As already approved by the ISMMS research pharmacy, study medication will be stored in [name] office in a locked cabinet. Thermostat will be set at all times to maintain acceptable storage temperature (59-86 °F). Throughout the week, temperature and humidity (current readings as well as min and max for both) will be logged daily on the study medication temperature log sheet (CRF13) using a Fisher Scientific digital Traceable Thermometer/Clock/Humidity monitor. Over the weekend, min and max temperature and humidity will be logged on the Monday following. Min and max temperatures are stored after the memory is cleared (once each day). [name] packages, dispenses, and maintains accountability for all study medication is assisted by the unblinded RC in packaging and distribution.

Study packets for randomization will be made from sealable envelopes. Each packet will contain sufficient medication for 8 weeks (one 60-dose mometasone twisthaler or one placebo metered dose inhaler MDI). Packets containing active medication will include 'protocol orientation module A' (a document that has training and usage instructions for the mometasone twisthaler). Packets containing placebo will contain 'protocol orientation module B' (a document that has training and usage instructions for the placebo inhaler). Each packet will also include 60 pain diaries. Packets will then be sealed and labeled with a code. The code will indicate which treatment arm the packet corresponds to. The unblinded RC will have access to a master list that reveals the coding scheme, SRC and PI will not have access to this list.

In the event that [name] is not present during study recruitment/enrollment, licensed nurse practitioner [name] will be present to oversee dispensation of study drug or placebo.

5.1 Recruitment, screening and eligibility procedures:

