6.1 Telephone follow up (week 2)

6.2 Overview

A follow up telephone call will be conducted 2 weeks after the patient is enrolled in the study. The goal of this phone call is to identify adverse events, to assess medication adherence, and pregnancy surveillance in female patients. Patients who become pregnant during the study will be asked to stop taking the medication and they will be withdrawn from the study. The phone script and event questionnaire (to assess for adverse events) is contained in CRF 2 – Adverse Events Form.

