7.1 Telephone follow up (week 4)

7.2 Overview

A follow up telephone call will be conducted 4 weeks after the patient is enrolled in the study. The goal of this phone call is to identify adverse events, to assess medication adherence, and pregnancy surveillance in female patients. Patients who become pregnant during the study will be asked to stop taking the medication and they will be withdrawn from the study. The phone script and event questionnaire (to assess for adverse events) is contained in CRF 2 – Adverse Events Form.

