8.1 In-person follow up (week 8)

8.2 Overview

The participant will be scheduled to return for an in-person follow up 8 weeks after study initiation. It is likely that the participant will also need to visit the clinic for standard care. If no visit is indicated, the visit will be conducted for purely research purposes without billing for medical care or utilization of any institutional services.

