- d. They answer yes to questions 12 , 14, 15 and >15 for question 13 in group 5

Investigator Approval of Eligibility: _____ Date: _____

Supplement 3: Inhaler training and adherence modules

(Affix Label Here)
 
Participant ID: _
	
Date Form Filled Out:
 
-----
 
day month year
	
Inhaled Mometasone to Promote Reduction of Vaso-occlusive Events

---	---	---

Protocol Orientation Module A

If you lose your medication

Contact study staff immediately:

[REDACTED]
[REDACTED]
[REDACTED]
[REDACTED]
[REDACTED]

Pain diaries

Pain diaries are included in your package. Try to fill out a pain diary every day. If you miss a day that's ok. You must fill out at least 30 diaries to stay in the study.

Your medicine

This package contains your medicine for this study. Take one puff of the medicine every day. The research coordinator will teach you how to use the inhaler.

(Affix Label Here) Participant ID: _____	Date Form Filled Out: - - - - - day month year	Inhaled Mometasone to Promote Reduction of Vaso-occlusive Events
--	--	--

**Protocol Orientation Module: Adapted from “BREATHE EASIER: AN
ADULT ASTHMA EDUCATION PROGRAM” and Mometasone
Package Insert**

“Breathe Easier”

Developed by the American Institutes for Research and
the Kaiser-Permanente Medical Group

National Heart, Lung, and Blood Institute

National Institutes of Health

National Asthma Education and Prevention Program

FOR ORAL INHALATION ONLY

Please read this leaflet carefully before taking this medication

This leaflet does not contain the complete information about this medication. If you have any questions about mometasone inhalation ask your health care provider or pharmacist.

IMPORTANT POINTS TO REMEMBER

- Use this medication regularly and at the same time each day, as prescribed by your health care provider. You or your child may not get the most benefit for 1 to 2 weeks or longer after starting the medication. If you or your child's symptoms do not improve in that time frame or if your condition gets worse, contact your health care provider.
- The cap is needed to use the TWISTHALER. Do not twist the mouthpiece with your hand. When the cap is removed from the TWISTHALER, the dose counter will count down by one, and show the number of doses available after this use.

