Let's take a few minutes to review inhaler use and make sure each of you is using the best technique.

How To Use YOUR INHALER

HOW TO USE ASMANEX TWISTHALER OR GIVE TO YOUR CHILD

- Remove the ASMANEX TWISTHALER from its foil pouch and write the date on the cap label.
- Throw away the inhaler 45 days after this date or when the dose counter reads “00”, indicating the final dose has been inhaled, whichever comes first.
- Follow steps 1 and 2 below each time you inhale a dose from your ASMANEX TWISTHALER.

Inhaler Parts:

[figure not shown]
See Figures 1 and 2 below to become familiar with the inhaler parts.

Step 1: Open inhaler

Hold the inhaler straight up (upright position) with the colored portion (the base) on the bottom (see Figure 3 below). It is important that you remove the cap of the TWISTHALER while it is in this upright position to make sure that you get the right amount of medicine with each dose.

Holding the colored base, twist the cap in a counterclockwise direction to remove it (see Figure 3 below). As you lift off the cap, the dose counter on the base will count down by one. Removing the cap loads the TWISTHALER with the medicine that you are now ready to inhale.

IT IS IMPORTANT TO NOTE that the indented arrow (located on the white portion of the TWISTHALER, directly above the colored base) is pointing to the dose counter (see Figure 2).

Step 2: Inhale dose

Breathe out fully. Then bring the TWISTHALER up to your mouth or your child's mouth with the mouthpiece facing toward you or your child. Place the mouthpiece in your mouth or your child's mouth, holding it in a horizontal (on its side) position as shown below (see *Figure 4*). Firmly close your lips around the mouthpiece and take in a fast, deep breath. Since the medicine is a very fine powder, you may not be able to taste, smell, or feel it after inhalation. Do not cover the ventilation holes while inhaling the dose.

[figure not shown]

Figure 4: Inhalation

Remove the TWISTHALER from your mouth and hold your breath for about 10 seconds, or as long as you comfortably can.

IMPORTANT: DO NOT BREATHE OUT (EXHALE) INTO THE INHALER.

After you take your medicine, it is important that you wipe the mouthpiece dry, if needed, and then **REPLACE THE CAP**, firmly closing the TWISTHALER right away (see *Figures 5 and 6* below).

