Be sure that the indented arrow is in line with the dose counter. Put the cap back onto the inhaler and turn it in a clockwise direction, as you gently press down. You'll hear a "click" to let you know that the cap is fully closed. This is the only way to be sure that your next dose is loaded the right way.

[figure not shown]

Figure 5: Closing the Inhaler

You'll hear a "click" to let you know that the cap is fully closed.

This is the only way to be sure that your next dose is properly loaded.

Figure 6: Closed Inhaler

IT IS IMPORTANT TO REPEAT STEPS 1 AND 2 EACH TIME YOU INHALE.

Rinse your mouth after using.

STORING YOUR INHALER

- Keep your inhaler clean and dry at all times. If the mouthpiece needs cleaning, gently wipe the mouthpiece with a dry cloth or tissue as needed. Do not wash the inhaler. Avoid contact with any liquids.
- **Store in a dry place at 25°C (77°F) [may range between 15-30°C (59-86°F)].**
- Keep your inhaler out of the reach of children.

HOW TO KNOW WHEN YOUR INHALER IS EMPTY

The inhaler has a dose counter on the colored base, which shows the number of doses left to use. As you lift off the cap to take your dose, the dose counter on the base will count down by one (if you began with the dose counter reading "30" this will cause the dose counter to now read "29"). Read the numbers from top to bottom.

When the unit reads "01" this indicates the last remaining dose. After dose "01" the counter will read "00". When you replace the cap, the unit will lock and then must be thrown away. Start using a new ASMANEX TWISTHALER as instructed by your health care provider.

Practical Solutions to Problems Using an Inhaler (10 minutes)

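### One 60-dose inhaler is counted as 8 weeks of active drug, but its leaflet says to discard it at day 45, about 11 days before the week-8 eNO and sVCAM measurement

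*Combined protocol and SAP*

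**What the plan says.** Section 4.3 (Study medication) sets the supply: "Each packet will contain sufficient medication for 8 weeks (one 60-dose mometasone twisthaler or one placebo metered dose inhaler MDI"). The same section puts Module A in active packets and Module B in placebo packets. Both modules give the dose: "Take one puff of the medicine every day".

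Module A (Supplement 3, instructions for using the Twisthaler) has the participant date the cap when the inhaler leaves its foil pouch. It sets a time limit and, as the alternative, a counter at zero: "Throw away the inhaler 45 days after this date or when the dose counter reads". The end of that sentence makes the earlier of the two binding: "indicating the final dose has been inhaled, whichever comes first". Its later example of reading the counter starts from 30 doses: "if you began with the dose counter reading" 30. Module B, as reproduced, has no time limit for discarding the inhaler.

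The contacts before the first refill are:

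- Section 6.2: "A follow up telephone call will be conducted 2 weeks after the patient is enrolled in the study".
- Section 7.2: "A follow up telephone call will be conducted 4 weeks after the patient is enrolled in the study".
- Section 8.2: "The participant will be scheduled to return for an in-person follow up 8 weeks after study initiation".

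The calls dispense nothing. Section 8.4 places the refill at the week-8 visit, and section 12.0 provides a replacement only when an inhaler is lost. Section 14.4 names change in eNO and sVCAM at 8 weeks as the Aim 2 primary outcomes. Adherence is read from dose counters, with a cutoff of at least 70% in section 8.5 and greater than 70% in section 14.6.

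**The concern.** Section 4.3 counts doses and ignores the in-use limit that the trial's own leaflet imposes. Someone who does exactly what both documents say runs out of usable drug before the visit at which the drug's effect is measured.

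Two things are at stake. First, the drug-free days come immediately before the eNO and sVCAM measurement and, on the text available, occur in the active arm only. If the effect fades once treatment stops, the estimated treatment difference moves toward zero. Second, good adherence is part of the feasibility outcome (sections 3.0 and 14.2). An active participant who discards early can miss fewer other doses and still pass, and the discarded inhaler may not be there for the unblinded coordinator to read at week 8.

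**Working it through.** **Inputs.** 60 doses per inhaler and an 8-week period (section 4.3); 1 dose a day (Modules A and B); discard at day 45 or counter 00 (Module A); calls at weeks 2 and 4 (sections 6.2, 7.2); visit and first refill at week 8 (sections 8.2, 8.4).

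**1. The plan's own figure.** Need: 8 × 7 = 56 doses. Supply: 60 ÷ 1 per day = 60 days. Since 60 ≥ 56, section 4.3 is right on dose count, with 60 − 56 = 4 doses spare.

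**2. With the discard rule.** Usable days = min(60, 45) = 45. Gap = 56 − 45 = 11 days, and 11/56 = 19.6% of the period. Doses left in the discarded inhaler = 60 − 45 = 15. The leaflet's counter example starts at 30; a 30-dose unit used once a day would be empty at day 30, before the limit applied. This suggests that the text was not adapted to a 60-dose, once-daily supply.

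**3. Sensitivity to timing.**

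- Pouch opened on day *o*, visit on day 56: gap = 11 − *o*. That is 4 days if opened on day 7 and none if opened on day 11.
- Pouch opened on day 0, visit on day *d* (56 or later): the part due to the leaflet is (*d* − 45) − max(0, *d* − 60). That is 11 days at *d* = 56, 15 at *d* = 60, and 18 − 3 = 15 at *d* = 63. It cannot exceed 15, because the doses run out at day 60 anyway.

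**4. Could a scheduled contact detect it?** The calls fall on days 14 and 28. The last is 45 − 28 = 17 days before the discard date, and 56 − 28 = 28 days then pass with no scheduled contact. Neither call can detect the gap.

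**5. Effect on the adherence measure.** The plan never gives the number of indicated doses. Taking 56, which follows from section 4.3 and the daily dose, 0.70 × 56 = 39.2, so 40 doses are needed under either wording of the cutoff. The alternative is to take the 60 doses in the inhaler as the denominator: 0.70 × 60 = 42, so 42 doses are needed for at least 70% and 43 for greater than 70%.

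| Denominator | Doses needed | Misses allowed, discards at day 45 | Misses allowed, does not discard |
|---|---|---|---|
| 56 | 40 | 45 − 40 = 5 | 56 − 40 = 16 |
| 60, at least 70% | 42 | 45 − 42 = 3 | 56 − 42 = 14 |
| 60, greater than 70% | 43 | 45 − 43 = 2 | 56 − 43 = 13 |

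A participant who takes every dose to day 45 and then discards scores 45/56 = 80.4%, or 45/60 = 75%. Discarding alone fails nobody, so restricting the analysis to adherent participants would not remove the gap.

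**6. Weeks 8 to 16.** If the refill is also one inhaler, which section 8.4 does not say, the gap recurs: 22 of 112 days over the treatment period.

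**7. What cannot be computed.** The documents give neither the share who would discard nor how fast eNO or sVCAM return toward baseline. No loss of power is therefore claimed.

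**The case against.** The strongest reply is that the consequence is conditional. A participant has to open the pouch promptly, date the cap, count 45 days and throw away a working inhaler that still shows 15 doses. The line looks like unedited manufacturer text, and the trial-specific page of Module A simply asks for daily use. The coordinator goes through the packet with the participant and explains how to reach staff with questions (section 5.3.4.7). The week-2 and week-4 calls cover adherence and could forestall the problem. The call script and the adherence and loss forms are listed but not reproduced, so they might deal with it. Finally, the primary outcome is feasibility, discarding alone fails nobody on adherence, and any bias in Aim 2 runs toward no effect.

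Much of this stands as a limit on size. The share who would discard is unknown, and the Aim 2 consequence may be small. It does not remove the conflict. The listed training topics are technique, dosing intervals and missed doses, with nothing about disregarding the discard line. No procedure covers a discarded inhaler, and forms that cannot be seen cannot be assumed to cancel a written instruction. Bias toward no effect is still bias in a primary Aim 2 comparison. The documents also cannot show whether the supply or the leaflet is in error, because the inhaler's in-use life is not stated elsewhere. Either way, the two texts cannot both stand.

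**Conclusion.** The concern holds. Followed as written, the plan leaves active participants without drug for 11 days before the week-8 measurement, assuming the pouch is opened on day 0 and the visit is on day 56. The range is from 0 days (opened on day 11) to 15 days attributable to the leaflet (opened on day 0, visit on day 60 or later). No text in the documents overrides the discard rule or resupplies a discarded inhaler before week 8.

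Confidence is high for the conflict between section 4.3 and Module A. The effect on eNO, sVCAM and the feasibility proportion is unknown; its direction for Aim 2, toward no difference, assumes that the effect wanes off drug. This should be fixed because it affects exposure just before a primary Aim 2 measurement and the correction is cheap.

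**What to change.** Settle the in-use life with the research pharmacy, then do one of the following:

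- Put a second inhaler in each 8-week packet, to be opened when the first reaches day 45, with a sentence telling participants not to use both at once.
- If the pharmacy confirms an 8-week in-use life for this inhaler, correct the discard line in Module A.

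Apply the same choice to the week-8 refill. Ask participants to bring every inhaler, including discarded ones, to the week-8 and week-16 visits, and sum the counters. If one is not returned, record an estimate of doses used, as section 12.0 already does for lost inhalers. State 56 indicated doses per 8-week period in both arms. The planned analyses need no change.

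**Cost.** No extra patients, visits or staff. The leaflet correction is one line. Second active inhalers for weeks 0 to 8: (2/3) × 45 = 30 at the planned sample size, or (2/3) × 56 ≈ 37 at the baseline number in Table 1. If the week-8 refill is also one inhaler, add (2/3) × 50 ≈ 33, for about 71 in total (37.3 + 33.3 = 70.7). Matching placebo packets, so that both arms handle two inhalers, brings the total to 56 + 50 = 106. The DSMB approves protocol amendments (section 1.4.3), and any CRF change, including a reminder in the week-4 call script, needs an IRB modification (section 13.3). A changed in-use limit should also be checked against the IND (section 15.3).
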